## 6.2 FIDELITY

### 6.2.1 INTERVENTIONIST TRAINING AND TRACKING

Fidelity assessments with the recovery coaches and hospital sites will ensure compliance with the POINT intervention design. A checklist of putative critical intervention components will guide the fidelity audit and feedback activities. We will conduct site visits at pre-implementation, early implementation (1 month following kick-off), mid-implementation (approximately 3 months), and late implementation (6 months). The day-long site visits will include interviews with clinicians and administrators, observation of POINT intervention, and review of records.

## 6.3 MEASURES TO MINIMIZE BIAS: RANDOMIZATION AND BLINDING

The study is randomized at the enrollment shift level. Each day of study enrollment is broken into three shifts (8am-3:59pm, 4pm-11:59pm, 12am-7:59am). In advance, each shift is randomly assigned to one of the two enrollment arms (i.e., POINT or control) to determine whether patients discharged during these times will enroll into the POINT arm or the standard care arm. Any individual who is cleared for discharge from the ED for an overdose or for an opioid-related health issue, including opioid withdrawal, abscess (from IV drug use) or active opioid intoxication will be eligible for the study. As determined by the preset randomization, recovery coaches (RC) will engage with patients cleared for discharged from the ED during the POINT shifts and research assistants (RA) will engage with patients cleared for discharged from the ED during control shifts.

Additional note: The study sites plan to implement Project POINT regardless of the research study. We are not modifying any aspect of POINT for the study purposes. Therefore, all recovery coach duties

(baseline administrative data collection, provision of naloxone, patient follow-up) are part of POINT prescribed services that would be carried out regardless of the research. We are randomizing the shift POINT is delivered on to take advantage of the fact that they are not able to fully staff all hospital shifts with a recovery coach--thus allowing us to test the intervention's effectiveness. Only those patients in the standard care arm will be asked to complete data collection activities that would not be completed outside of the research study.

Sample randomization for week of services								
Week	Shift	Day						
		Mon	Tue	Wed	Thu	Fri	Sat	Sun
1	8am-3:59pm	RC	RA	RA	RC	RC	RC	RA
	4pm-11:59am	RA	RC	RC	RA	RA	RA	RC
	12am-7:59am	RC	RA	RA	RC	RA	RA	RC

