## 4 STUDY DESIGN

### 4.1 OVERALL DESIGN

The primary objective of this pragmatic clinical trial is to replicate POINT at two new hospitals and establish POINT's effectiveness compared to standard care. In doing so, we aim to understand POINT's effect on the recovery process, including treatment and recovery outcomes and overdose. We hypothesize that POINT patients will engage in MOUD at higher rates, remain in treatment longer, and have significantly improved outcomes in comparison to the standard care group.

Hospital patients meeting the eligibility criteria at one of the two participating EDs are approached by a recovery coach or research assistant and invited to enroll in the study. Participants of the study are randomly enrolled into one of two study arms: (1) the POINT intervention arm, in which they receive ongoing recovery support services from a recovery coach or (2) the control arm, in which they receive a list of available local resources for substance use disorder from the research assistant. The study utilizes shift-level randomization, and each day of enrollment is separated into three enrollment shifts which are randomly assigned to one of the two study arms. Thus, participants' arm assignment is pre-determined by the shift in which they are discharged from the ED and enrolled into the study.

Participants are asked to complete a single structured interview at the time of their enrollment and are followed longitudinally only through administrative data, which is collected for participants from three years prior to their enrollment through two years following their enrollment.

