## 9.2 SAMPLE SIZE DETERMINATION

Our goal is to obtain a total of 356 patients in each study arm ( $n = 712$ ) by Month 32, which will provide us with enough patients to obtain a full year of follow-up data to detect a minimum 6% reduction in our primary outcome (subsequent overdose) at 80% power, assuming a 12% rate of subsequent overdose for the standard care arm at the 5% significance level (this is a conservative calculation based on observed subsequent overdose rates at Eskenazi and Indianapolis Emergency Medical Services).

(Note: This goal was not ultimately reached due research activities needed to stop because of the COVID-19 pandemic. Researchers developed an alternative plan to assess outcomes using a retrospective case control design that was approved by the funder. However, all planned analyses were conducted using data collected from patients who were enrolled in the trial.)

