The secondary analysis involves comparing outcome measures pre- and post-ED discharge for POINT patients. Binary outcomes including child welfare involvement will be compared using the McNemar's test and the continuous outcome including the days of incarceration will be compared using the Wilcoxon signed rank test due to the skewness of the data. Additional analyses will be conducted to account for patient characteristics in the comparison between the POINT and standard care arms using logistic regression for binary outcomes, Poisson regression for length of MOUD treatment, and Cox proportional hazards model for time to relapse. For the comparison pre- and post-ED discharge in the POINT arm, generalized estimating equations approach will be performed using logistic regression for Medicaid enrollment and child welfare involvement and Poisson regression for days of incarceration. Hospitals will be included in the models as a fixed effect to account for the potential differences in patient population across hospitals.

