#### 9.4.2 ANALYSIS OF THE PRIMARY ENDPOINT(S)

Questions	Defined/explained
Primary endpoint	
Describe how the primary endpoint is calculated, if not readily apparent	Change in Overdose Admissions: Using electronic health records, it is calculated as the total combined number of overdoses resulting in an emergency department presentation within the specified time period.
Describe the scale (nominal/binary/categorical, ordinal, interval); state if it is measured as a single endpoint/summary measure or repeated measure	binary
Describe the statistical procedure(s) that will be used to analyze the primary endpoint (e.g., multiple regression, repeated measures mixed models, logistic regression, Analysis of Covariance (ANCOVA)). Describe the covariates and factors in the model. Provide a rationale for covariates and how they will be selected to achieve a parsimonious model. If the decision to specify covariates is deferred for the SAP, indicate here.	Summarized using frequencies and percentages and then compare arms using the Fisher's exact test.
Describe how results of statistical procedure(s) will be presented (e.g., adjusted means (Least-squares means (LSMEANS)) with standard errors, odds ratios with 95% confidence intervals, prevalence rates, number-needed-to-treat)	Presented using frequencies and percentages
Describe details to check assumptions required for certain types of analyses (e.g., proportional hazards, transformations or, when appropriate, nonparametric tests)	The nonparametric Fisher's exact test is used to compare the primary endpoint.
Describe the Populations for which the analysis will be conducted, as discussed in Section 9.3, Populations for Analyses	All study participants
Describe how missing data will be handled (e.g., type of imputation technique, if any, and provide justification), and approach to handling outliers, non-adherence and lost to follow-up	We do not expect there to be a large amount of missing data due to the use of administrative datasets. However, missing values may occur when subjects die during the specified time period. Sensitivity analysis is performed by excluding subjects who die during the specified time period.

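### Arms are assigned by enrollment shift, but the sample size and the primary Fisher test treat patients as individually randomised; the likely effect is small, and the planned test has about 77% power, not 80%

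*Combined protocol and SAP*

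**What the plan says.** Section 4.1 says "The study utilizes shift-level randomization" and that "participants' arm assignment is pre-determined by the shift in which they are discharged from the ED and enrolled into the study". Section 6.3 repeats this: "The study is randomized at the enrollment shift level", with three eight-hour shifts a day allocated in advance to a recovery coach (POINT) or a research assistant (control).

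Section 9.2 sets the target: "Our goal is to obtain a total of 356 patients in each study arm", in order "to detect a minimum 6% reduction in our primary outcome (subsequent overdose) at 80% power", with a 12% control rate and a 5% significance level. It gives no ICC, number of patients per shift or design effect.

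Section 9.4.2 describes the primary analysis as "Summarized using frequencies and percentages and then compare arms" by Fisher's exact test. In section 9.4.1, "Hospitals will be included in the models as a fixed effect" applies to the regression models, not to the primary test. GEE is planned only for the pre/post comparison within the POINT arm. Shift appears in none of the analyses, and nothing explains why it can be left out.

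**The concern.** Patients enrolled in the same shift at a hospital share an arm by design, and they also share a time of day and the type of staff who recruited them. If their outcomes are correlated, a patient-level test understates the variance of the arm difference and the sample size is too small. Fisher's exact test needs no distributional assumption about the outcome, but it does assume independent patients.

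Two things are at stake: whether the primary p-value reflects how the arms were assigned, and whether the stated power belongs to the test that will be used.

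**Working it through.** **1. The plan's own figure.** Inputs from section 9.2: 12% v 6% (a 6-point absolute reduction), 80% power, 5% significance. Sidedness is not stated; two-sided is assumed. With mean rate 0.09:

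n = [1.96 × √(2 × 0.09 × 0.91) + 0.8416 × √(0.12 × 0.88 + 0.06 × 0.94)]² / 0.06² = 355.9, so **356 per arm**, with 80.0% power.

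This matches exactly. Other variants do not: unpooled variance gives 354, arcsine 348, continuity-corrected 389 and one-sided 281. Reading the 6% as a relative reduction gives 31,144. The formula used therefore had no continuity correction and a design effect of 1.

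**2. Patients per shift (assumed, as the documents do not give it).** Take enrollment over all 32 months: 32 × 30.4375 × 3 = 2,922 shifts.
- One schedule covering both hospitals: 712 / 2,922 = 0.244 per shift.
- Each hospital's shifts counted separately for the full period: 712 / 5,844 = 0.122.
- Allowing for the second hospital joining in October 2018 (assumed dates 14 February 2018 and 16 October 2018 to 1 October 2020): 2,880 + 2,148 = 5,028 site-shifts, so 712 / 5,028 = 0.142.

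**3. Design effect.** With Poisson arrivals at mean λ per shift, an enrolled patient sits on average in a shift of size 1 + λ, so DE = 1 + λ × ICC. If enrollment falls in a fraction f of shifts, DE = 1 + λ × ICC / f. The ICC range of 0.01 to 0.10 is assumed.

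| λ | All shifts, ICC 0.01 | All shifts, ICC 0.10 | One tenth of shifts, ICC 0.10 |
|---|---|---|---|
| 0.122 | 1.001 | 1.012 | 1.12 |
| 0.142 | 1.001 | 1.014 | 1.14 |
| 0.244 | 1.002 | 1.024 | 1.24 |

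At DE 1.024, the sample size is 356 × 1.024 = 364.5, or 365 per arm, and power at 356 per arm is about 79%. At DE 1.14, the effective size is 356 / 1.14 = 312 per arm, with about 74.6% power for a test that accounts for clustering.

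**4. The planned test.** Exact enumeration of the two-sided Fisher test at 356 per arm gives:
- size 3.76% when both arms are at 12%;
- power 77.1% for 12% v 6% (77.6% at 360 per arm, 81.2% at 390).

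**5. Fisher's size under clustering.** A size of 3.76% corresponds to a normal critical value of 2.079. The approximate size under clustering is 2 × [1 − Φ(2.079 / √DE)]: 4.0% at DE 1.024, 4.7% at 1.10, 5.1% at 1.14 and 6.2% at 1.24. It passes 5% at DE = (2.079 / 1.96)², about 1.13.

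**The case against.** The strongest reply is that shift clustering does almost nothing here. Most enrolled patients would be alone in their shift, and Fisher's conservatism more than absorbs a design effect of 1.00 to 1.02. That stands, and it limits the weight of the point. It does not remove it: the plan neither makes this argument nor asks for the patients-per-shift figure that would support it. Fisher's conservatism is also unconnected to the allocation, and it lowers power.

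A second reply is timing. The note in section 9.2 says the planned analyses were conducted on the enrolled patients, so replacing the primary test now would be post hoc. That also stands and shapes the fix.

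Several stronger readings are tempting but not supported:

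- *The Fisher p-value is invalid.* Under full-period enrollment its approximate size stays near 4%. It exceeds 5% only when enrollment is highly concentrated and the ICC is at the top of the assumed range.
- *Clustering by recovery coach makes the problem large.* The documents give no number of coaches, caseload or ICC, so any size would be wholly assumed. It is also a separate question that clustering by shift would not answer.
- *A design-based test costs no power.* At DE 1.14 it has about 74.6%, against about 75.6% for Fisher under the same clustering.
- *The shift of every participant is already on file.* The data items listed in section 8.1 do not include a shift identifier.
- *Each hospital had its own schedule.* Section 6.3 shows one sample grid and mentions no stratification by hospital.

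**Conclusion.** The mismatch between design and analysis is real and unexplained: shifts are randomised, while the sample size and the primary test treat patients as individually randomised and omit shift and hospital. From shift clustering alone the harm is probably small, with a design effect of about 1.00 to 1.02 and a loss of at most about one point of power. It reaches about 1.14 (1.12 to 1.24 across the three shift counts) only if enrollment sits in a tenth of shifts and the ICC is 0.10. These figures rest on assumed ICCs, enrollment dates and arrival pattern, and on a target of 712 that section 9.2 says was not reached.

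The power shortfall does not depend on those assumptions. At the planned 356 per arm and the plan's own rates, two-sided, the Fisher test has about 77% power, not 80%. That follows from pairing an uncorrected normal formula with an exact test, not from shift randomisation. Overall this is a worthwhile improvement to the plan, not a fault that overturns the trial's result.

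**What to change.** In section 9.4.2, add a shift-clustered analysis of the primary endpoint. Either of these would serve:
- a logistic or risk-difference GEE with robust variance by shift and hospital as a fixed effect; or
- a permutation test that re-randomises shifts under the actual allocation scheme. The scheme should be written down first: in the sample grid the first two shifts are in opposite arms on all seven days, so allocation may have been restricted within day and a free permutation could be wrong.

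If this is specified before analysis, make it the main test. If the planned Fisher analysis has already been run, keep Fisher and report the clustered result beside it as a labelled sensitivity analysis.

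Report the distribution of enrolled patients per shift. In section 9.2, state the design effect used (1, with its justification, or another value), and either restate power as about 77% for Fisher or recalculate it for the test chosen.

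The cost is slightly more analysis and the retrieval of a masked shift code. Because the analysis data are de-identified, that code may have to be derived from the enrollment time or the schedule before release.

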### 5.5 STRATEGIES FOR RECRUITMENT AND RETENTION

Individuals who are admitted to the ED for either an opioid overdose OR an opioid-related health issue will be deemed initially eligible, and the research personnel will be alerted of their presence in the ED. Research staff will also verify that the patient is at least 18 years of age. Once the initial eligibility is determined per the medical staff (reason for admission and at least age 18), either the recovery coach or the research assistant will approach the patient to inform them of study. This interaction will occur in the room in which they are receiving care in the ED, which is confidential area of the ED. They will use this initial meeting to explain the study and to ask the patient the questions from the opioid use disorder screening tool. If the patient scores at least a "1" on the opioid use disorder screening tool, they will be initially eligible for the study. They will then provide a brief overview of who they are and what the POINT study involves.

Because this initial interaction will occur prior to their discharge clearance, the research staff or recovery coach will reiterate to the patient that the research study is not a part of the treatment plan, and the patient may decline the study without impacting their treatment. Further, this "pre-discharge clearance" interaction will not hinder the discharge process; rather, we will utilize the "down time" the patient experiences while waiting in the ED. Once this initial discussion is complete, and if the patient chooses to take part, the research staff will return to the patient once he or she has received medical clearance for discharge from the ED and will move forward with the consent process.

Participants receive a \$30 gift card for their participation in the study. Research staff or recovery coaches will inform patients of this while explaining the study to the patient. The incentive is received at the end of their study visit.

Retention strategies are not applicable to the study, as participant will only be followed longitudinally through secondary administrative data.

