##### 10.1.1.2 CONSENT PROCEDURES AND DOCUMENTATION

Once the patient is determined to meet all the initial eligibility criteria, the research team member will begin informed consent. Informed consent is a process that is initiated prior to the individual's agreeing to participate in the study and continues throughout the individual's study participation. Consent forms will be Institutional Review Board (IRB)-approved and the participant will be read the document by a recovery coach or research assistant and review the document. The study team member will explain the research study to the participant and answer any questions that may arise. A verbal explanation will be provided in terms suited to the participant's comprehension of the purposes, procedures, and potential risks of the study and of their rights as research participants.

We will not fully disclose the purposes of the research to the standard care arm because (1) Methodist Hospital and Ball Memorial were planning on implementing POINT outside of the context of this study and because their ability to staff recovery coaches is limited anyway, we are not creating any disparity in patients ability to access point that would not naturally exist and (2) we are concerned that full disclosure of the purposes would unnecessarily upset the control arm patients who might desire the services after learning of them.

Participants will have the opportunity to carefully review the written consent form and ask questions prior to signing. The participant will sign the informed consent document prior to data collection beginning. Participants must be informed that participation is voluntary and that they may withdraw from the study at any time, without prejudice. A copy of the informed consent document will be given to the participants for their records. The rights and welfare of the participants will be protected by emphasizing to them that the quality of their medical care will not be adversely affected if they decline to participate in this study.

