#### 10.1.8 QUALITY ASSURANCE AND QUALITY CONTROL

In addition to required CITI trainings, to ensure adherence to research protocols, the principal investigator and project manager will conduct a required training for all study personnel involved in the enrollment and data collection processes. During this training, the PI and project manager will provide a detailed overview of the study purpose and the enrollment procedures, including the eligibility criteria, screening process, enrollment script, and informed consent procedures. They will also discuss the data collection procedures in detail, during which they will read through the data collection questionnaire and complete mock interviews with study personnel. Subsequently, during the first two weeks of study enrollment, the PI, project manager, or senior research staff will shadow all study personnel during consent and data collection activities to ensure protocol adherence.

Throughout the course of the study, the project manager will monitor enrollment adherence using the Emergency Medical Services (EMS) Patient Tracker system. The system will send daily automated reports to the project manager to indicate which EMS runs involving naloxone administration were taken to the hospitals involved in the study. The project manager will then look up the names of the patients who received naloxone and compare these names with the enrollment records; any missed patients will be noted in our tracking records and, if necessary, the project manager will follow-up with study personnel. To ensure consent and data collection procedures are properly followed and potential issues are promptly addressed, the PI and project manager will conduct monthly teleconference calls with all study personnel. They will discuss current enrollment and potential concerns regarding enrollment, consent documents, or data collection procedures and tools. Further, the project manager will touch base one-on-one with all study personnel at least once every month to address any specific issues.

Lastly, we will review all data collection packets, including consent documents and health information releases, to ensure proper completion. All data collection records in REDCap will be reviewed by the project manager to check for accuracy and completion. Revisions to the data collection forms will be completed as necessary.

---

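### Recruiters know the arm and differ between arms, so the enrolled groups may not be comparable, yet the primary test is unadjusted and the adjusted analysis names no patient covariates

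*Combined protocol and SAP*

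**What the plan says.** **Allocation.** Section 6.3 randomises eight-hour shifts: "In advance, each shift is randomly assigned to one of the two enrollment arms". Section 4.1 confirms that "participants' arm assignment is pre-determined by the shift in which they are discharged from the ED and enrolled into the study". No step is described that hides the schedule from recruiting staff.

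**Who recruits.** Under section 6.3, "recovery coaches (RC) will engage with patients cleared for discharged from the ED during the POINT shifts", while "research assistants (RA) will engage with patients cleared for discharged from the ED during control shifts". According to sections 5.5, 8.1 and 10.1.1.2, coaches and assistants carry out the approach, the opioid use disorder screen, the competency questions and consent.

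**What patients are told.** Section 10.1.1.2 states: "We will not fully disclose the purposes of the research to the standard care arm". One reason given is that control patients might want the services if they heard of them.

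**Who is analysed.** Section 9.3 includes everyone who consented.

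**How arms are compared.** For the primary endpoint, section 9.4.2 says: "Summarized using frequencies and percentages and then compare arms", by Fisher's exact test. Section 9.4.1 adds logistic regression on patient characteristics, with hospital as a fixed effect, as a further analysis. It does not list the characteristics. Section 9.4.5 compares baseline characteristics but attaches no consequence to the result.

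**Order of contact.** Section 5.5 has staff ask the screening questions at a first meeting and notes that "this initial interaction will occur prior to their discharge clearance". Section 8.1 requires clearance to be confirmed before screening.

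**Monitoring.** Section 10.1.8 compares emergency medical services (EMS) naloxone runs with enrolment records, and "any missed patients will be noted in our tracking records".

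**The concern.** Randomising shifts protects the comparison of all eligible patients who come up for discharge. The analysis set is smaller: those who agreed after an approach by staff who knew the arm, were a different type of staff in each arm, and worked under a different level of disclosure. If agreeing to enrol is linked to overdose risk differently in the two arms, the arms differ in risk at baseline. An unadjusted test then mixes that difference with any effect of POINT. A small p-value could reflect selection, and a real benefit could equally be hidden. The plan leaves its one defence, the adjusted model, outside the primary analysis and without named patient covariates.

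**Working it through.** **1. The plan's own figure.** Section 9.2 gives 12% against 6%, 80% power and a 5% level. Taken as two-sided, with pooled variance and mean rate 0.09:

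n = [1.960·√(2·0.09·0.91) + 0.842·√(0.12·0.88 + 0.06·0.94)]² / 0.06² = (0.793 + 0.339)² / 0.0036 ≈ 356 per arm.

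This matches, so the sample size is not in question. By exact enumeration at 356 per arm, the two-sided Fisher test has 77.1% power. With 12% in both arms it rejects 3.8% of the time, of which 1.9% favours POINT.

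**2. Illustration with no intervention effect.** These assumptions are not in the documents:
- 40% of eligible patients have a one-year overdose risk of 20% and 60% have 6.7%. Overall: 0.4·20% + 0.6·6.7% = 12%, the planning rate.
- Assistants enrol 60% of both groups.
- Coaches enrol a share c_H of the high-risk group and c_L of the low-risk group.

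High-risk share among enrolled POINT patients: w = 0.4·c_H / (0.4·c_H + 0.6·c_L). POINT rate = 20%·w + 6.7%·(1 − w).

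| c_H / c_L | w | Overall coach enrolment | POINT rate | Gap from 12% |
|---|---|---|---|---|
| 60% / 60% | 0.24/0.60 = 0.400 | 60% | 12.0% | 0 |
| 50% / 65% | 0.20/0.59 = 0.339 | 59% | 11.2% | 0.8 points |
| 45% / 70% | 0.18/0.60 = 0.300 | 60% | 10.7% | 1.3 points |
| 40% / 70% | 0.16/0.58 = 0.276 | 58% | 10.3% | 1.7 points |

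The spurious gap is 14% to 28% of the 6-point target.

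**3. Effect on the planned test.** Exact enumeration of the two-sided Fisher test:

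| c_H / c_L | Falsely favours POINT, 356 per arm | Any rejection, 356 per arm | Falsely favours POINT, 100 per arm (assumed) |
|---|---|---|---|
| 60% / 60% | 1.9% | 3.8% | 1.5% |
| 50% / 65% | 4.1% | 4.8% | 2.3% |
| 45% / 70% | 6.4% | 6.8% | 3.0% |
| 40% / 70% | 8.3% | 8.6% | 3.6% |

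The 100-per-arm column is included because section 9.2 says planned enrolment was not reached and gives no achieved number.

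**4. Other assumptions.** Take two risk groups at 18% and 6%, with 60% high-risk in control and 40% in POINT. The rates are 13.2% and 10.8%, a gap of 2.4 points, and Fisher's test rejects 13.8% of the time. With groups at 16% and 8% it rejects 8.0%; at 20% and 4%, 22.2%. In the 18%/6% case, a Cochran-Mantel-Haenszel test stratified on the risk group stays at about 5.0% (40,000 simulated trials), but only because the factor is measured and used.

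**5. Direction.** Swapping the two mixes reverses the sign: the same imbalance then favours control or masks a benefit.

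**The case against.** **The plan is not wholly unadjusted.** Section 9.4.1 has the logistic model, section 9.4.5 compares baseline, and outcomes come from administrative records. This stands in part. The model is not primary and its patient covariates are open. Administrative outcomes limit biased ascertainment, not biased enrolment.

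**The selection rates are invented.** True. The documents give no approach or consent figures by arm. A reader might infer that the comparison is biased towards POINT; nothing in the documents shows that selection occurred, or in which direction.

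**The inflation can be overstated.** A reader using a normal-approximation test would get about 5% to 10% against 2.5%. The planned test is Fisher's, which is conservative here. The mildest scenario keeps total rejection at 4.8%, and smaller arms reduce the inflation further.

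**How the offers differed is partly inference.** Section 8.1 describes a recruitment script, and section 6.1.2 starts the discussion of recovery support after enrolment. The different recruiters and the different disclosure are explicit; what coaches said about POINT before consent is not.

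**Contact across shifts may be rare.** A reader might take it as a feature of the whole trial. The amendment history dates introduction before clearance to version 7 (2/6/20), and consent still waited for clearance. The contradiction between sections 5.5 and 8.1 nevertheless remains in the current text.

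**Adjustment cannot finish the job.** Correct: willingness to accept a coach is not in the administrative data.

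**Conclusion.** The route to selection is documented: allocation known before approach, different recruiters, different disclosure, and analysis of consenters only. Shift randomisation therefore does not guarantee comparable enrolled arms, and the primary analysis does nothing to offset this. Size and direction cannot be established from the documents. Under the stated assumptions, the chance of a false finding for POINT roughly doubles to quadruples at 356 per arm (4.1% to 8.3% against 1.9%). It rises more modestly at an assumed 100 per arm (2.3% to 3.6% against 1.5%).

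The documents do not support the stronger readings that the randomisation failed or that a benefit would be spurious. Nor would similar consent rates be reassuring: in the illustration coaches enrol 58% to 60% overall against 60% for assistants, while the risk mix differs. This should be corrected in the analysis plan and in the wording of the conclusions.

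**What to change.** 1. Make the main between-arm analysis a logistic regression adjusted for named baseline data: ED overdoses in the prior year, MOUD in the prior year, reason for the index visit, hospital and shift slot. Keep Fisher's test as a supporting analysis. The records and interview listed in section 8.1, with the enrolment record, supply these.
2. Compare these risk factors by arm, reporting the size of the differences.
3. Report whatever approach and consent counts exist by arm. Say that the section 10.1.8 tracking covers only EMS naloxone runs, so it would not systematically capture patients with withdrawal, abscess or endocarditis, and that similar consent rates do not rule out selection.
4. State that unmeasured selection limits a causal reading.
5. Reconcile sections 5.5 and 8.1 on screening before clearance. If the shift of first approach was recorded, add a sensitivity analysis excluding patients whose first approach and clearance fell in shifts of different arms. If it was not recorded, say so.

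**Cost.** Analysis-plan wording and modest analysis time, with no new data collection. With few patients the model may be sparse: 200 patients at 12% give 24 events for about seven terms (arm, two prior-year variables, visit reason, hospital, two for slot). A rule for that case, such as Firth's penalised likelihood, should be stated with the model. Section 9.2 describes the analyses as already conducted; if so, the adjusted model should be labelled as added afterwards. The claim becomes more cautious.
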